9.2 SETTING

Please see section [9.1](#).

9.2.1 Study sites

Please see section [9.1](#) and [9.4](#)

9.2.2 Study population

Please see section [9.1](#).

9.2.3 Study visits

Not applicable

9.2.4 Study discontinuation

Boehringer Ingelheim reserves the right to discontinue the study overall or at a particular study site at any time for the following reasons:

1. Failure to meet expected enrolment goals overall or at a particular study site
2. Violation of Good Pharmacoepidemiology Practice (GPP), the study protocol, or the contract by a study site, investigator, or research collaborator, disturbing the appropriate conduct of the study

The investigator/the study site/research collaborator will be reimbursed for reasonable expenses incurred in case of study/site termination (except in case of the third reason).

9.3 VARIABLES

9.3.1 Exposures

The exposure variables are Tio use vs. LABA use in combination with ICS. The operational definitions are provided in the sections above. After PSM, the cohort group will be the key predictor for the Cox PH regression to assess the primary outcome.

Proprietary confidential information © 2021 Boehringer Ingelheim International GmbH or one or more of its affiliated companies

9.3.2 Endpoints

9.3.2.1 Primary endpoints

[figure not shown]
The primary endpoint measure is time to first severe exacerbation. Severe exacerbations will be defined as:

- A hospitalization with a primary diagnosis of asthma or
- An ER visit with a primary diagnosis of asthma

9.3.2.2 Secondary endpoints

Secondary endpoints will include:

- Time to first moderate-or-severe exacerbation
 - Any systemic corticosteroid use or
 - A hospitalization with a primary diagnosis of asthma or
 - An ER visit with a primary diagnosis of asthma
- Proportion of patients with exacerbation
- Rate of exacerbation at 6 months and one year
- Proportions of patients with Health care resource utilization (HCRU). HCRU is defined as hospitalizations, emergency room (ER) visits, and outpatient visits during follow-up, all-cause and asthma related.
- Mean monthly HCRU (including frequency of hospitalizations, ER visits, OP visits)
- Proportion of patients with use of rescue medications (defined as patients with one or more SABA claims during the follow-up period)

9.3.3 Covariates

The covariates included in the PSM will be

- Gender
- Age group
- Region
- ICS dose level
- Control level
- Rescue medication use
- Comorbidities included in the Charlson Comorbidity Index
- ICS history (yes/no)
- ICS history duration
- Season of index date
- Index year
- Baseline all-cause resource use (presence vs. absences of hospitalizations, or ER visits, or outpatient visits)
- Baseline other asthma medications (use vs. no use)

Proprietary confidential information © 2021 Boehringer Ingelheim International GmbH or one or more of its affiliated companies

- Baseline overall medication history (polypharmacy defined as number of unique medications)
- Insurance type
- Hypertension
- Gastroesophageal reflux disease
- Allergic Rhinitis
- Obesity
- Sinusitis
- Obstructive sleep apnea
- Cardiovascular disease
- Diabetes
- Renal failure
- Arthritis
- Osteoporosis
- Depression
- Cancer (excluding basal cell carcinoma)
- Baseline pneumonia diagnosis
- Baseline acute bronchitis diagnosis
- Diagnosis of dyspnea during baseline identified using ICD 9 786.0x and ICD 10 R06.0x
- Diagnosis of alcohol dependence during baseline identified using ICD 9 303.xx, 305.0x and ICD 10 F10.xx
- Smoking dependence during baseline identified using ICD 9 305.1 and ICD 10 F17.xx

In addition to the key independent variable of interest (ICS+TIO vs ICS/LABA group), we will include time varying medication exposure as a covariate in the regression.

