9. RESEARCH METHODS

9.1 STUDY DESIGN

1. Patients with least two asthma diagnosis (ICD 9 CM: 493.xx or ICD 10: J45-J45.999) will be included.
2. Patients will be required to be concurrently on ICS+Tiotropium (specifically Tiotropium Respimat® 1.25 mcg) or ICS/LABA.
3. Patients with least two diagnosis of COPD at any time during the study period will be excluded.
4. Patients less than 12 years of age will be excluded.
5. Patients will be required to have enrollment for at least 6 months prior to ICS+Tio or ICS/LABA use.
6. Patients on biologics within 6 months prior to ICS+Tio or ICS/LABA use will be excluded.
7. Patients with prior Tio or ICS/LABA use during the 6-month baseline period will be excluded.
8. Patients with urinary bladder obstruction, urinary retention, and glaucoma will be excluded.
9. After the PSM process, unmatched patients will be excluded.

Patients will be classified into two groups based on the exposure on the index date: 1. ICS+Tio; and 2: ICS/LABA. The date of concurrent medication initiation will be defined as the index date based on the date of the first prescription claim defining their add-on medication. We will record various baseline measures, including demographics such as gender, age, and region, comorbidity level defined using Charlson Comorbidity Index (CCI), other specific comorbidities not included in the CCI ([Table 1](#)), inhaled medication use, and control level as defined in Table 1. Additionally, we will classify patients based on their daily ICS dose levels as 'low dose ICS', 'medium dose ICS', and 'high dose ICS'. The dose levels will be assigned per GINA 2020 criteria (Global Initiative for Asthma. Global Strategy for Asthma Management and Prevention 2020). Medications that are available with only two dose level indications will be tagged as 'low' for the lower of the two dose levels, and 'high' for the highest dose level.

Proprietary confidential information © 2021 Boehringer Ingelheim International GmbH or one or more of its affiliated companies

Table 1: Baseline Parameters and Variable Definitions

Variable Name and Type	Description and Definition	Covariate Adjustment Method
Demographics	Age (5-year increments), Gender,	PSM
Region	Region (Northeast, Midwest, South, West)	PSM
CCI	Charlson Comorbidity Index score	PSM
Inhaled medication use	Identified using unique claims during the baseline period	PSM

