Control Status: Not Well Controlled or Well Control	
“Not Well Controlled” if patient has any one of the following events
 
 • Prescription for OCS • Asthma-related ER • Asthma-related hospitalizations 
“Well controlled” if patient has none of the above events
 
(Ref: Stempel JACI 2005)
	PSM
ICS history	Defined by use of ICS monotherapy prior to index date	PSM
ICS history duration	Days on ICS monotherapy prior to index date	PSM
ICS dose level	Daily dose of ICS classified as low dose ICS, medium dose ICS, and high dose ICS	PSM
Season	Season of cohort entry (Summer, Spring, Fall, Winter)	PSM
Index year	Year of the index date	PSM
All-cause resource use	All-cause hospitalizations, ER visits, outpatient visits	PSM
Other asthma medications	Leukotriene modifiers	PSM
Medication history	Polypharmacy calculated based on number of unique medications	PSM
Insurance type	Identified using payer type data field	PSM
Hypertension	Identified using appropriate ICD codes. Coded as binary (yes/no) variables	PSM
Allergic rhinitis	Identified using appropriate ICD codes. Coded as binary (yes/no) variables	PSM
Sinusitis	Identified using appropriate ICD codes. Coded as binary (yes/no) variables	PSM
Obstructive sleep apnea	Identified using appropriate ICD codes. Coded as binary (yes/no) variables	PSM
Gastro-esophageal reflux disease	Identified using appropriate ICD codes. Coded as binary (yes/no) variables	PSM
Obesity	Identified using appropriate ICD codes. Coded as binary (yes/no) variables	PSM
Cardiovascular disease	Identified using appropriate ICD codes. Coded as binary (yes/no) variables	PSM
Diabetes	Identified using appropriate ICD codes. Coded as binary (yes/no) variables	PSM

Proprietary confidential information © 2021 Boehringer Ingelheim International GmbH or one or more of its affiliated companies

Table 1: Baseline Parameters and Variable Definitions (cont)

Variable Name and Type	Description and Definition	Covariate Adjustment Method
Renal failure	Identified using appropriate ICD codes. Coded as binary (yes/no) variables	PSM
Arthritis	Identified using appropriate ICD codes. Coded as binary (yes/no) variables	PSM
Depression	Identified using appropriate ICD codes. Coded as binary (yes/no) variables	PSM
Osteoporosis	Identified using appropriate ICD codes. Coded as binary (yes/no) variables	PSM
Cancer (excluding basal cell carcinoma)	Identified using appropriate ICD codes. Coded as binary (yes/no) variables	PSM

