9.7 DATA ANALYSIS

9.7.1 Main analysis

Sample attrition at each step of the inclusion-exclusion criteria will be provided. We will develop the breakdown of the distribution of demographic, comorbidity, and baseline measures prior to and after the PSM (unmatched and matched cohorts). Significance of differences will be tested at $P<0.05$ for the matched cohort. Additionally, we will consider the use of standardized mean differences as noted above, in which $SMD <0.1$ indicates balance of baseline covariates. The primary endpoint measure is time to first severe exacerbation and severe exacerbation will be defined as a hospitalization or an ER visit with a primary diagnosis of asthma. We will calculate the time in days to first exacerbation. Also, as part of the primary end point analysis, we will develop KM curves based on initial exposure and conduct time varying Cox proportional hazards modeling accounting for changes in exposure status over the follow up time to estimate the risk of exacerbation between ICS+Tio vs. ICS/LABA. Secondary endpoints will include a number of measures. We will calculate the time in days to first moderate-or-severe exacerbation defined as use of systemic corticosteroid or a hospitalization or ER visit with a primary diagnosis of asthma. KM curves based on initial exposure and time varying Cox PH models will be conducted for this secondary end point as well. We will also calculate and compare the rate of exacerbation, proportion of patients with exacerbations after 6 months and one year among the sub-population of patients having at least 6 months and a year of follow-up, respectively. We will report rates in patient-years to account for variable follow-up time. We will also compare the mean monthly (to account for variable follow-up time) per patient HCRU (all-cause and asthma related hospitalizations, ER visits, and outpatient visits) during the follow-up period, between the two groups. Proportions of patients with and without rescue medication use will be compared between the two groups as well.

Proprietary confidential information © 2021 Boehringer Ingelheim International GmbH or one or more of its affiliated companies

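### Mean monthly HCRU is a visit-frequency endpoint, but baseline resource use is matched only as present or absent; matching on baseline visit counts is a cheap improvement.

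*Combined protocol and SAP*

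**What the plan says.** Section 9.3.2.2 lists two kinds of HCRU endpoint. One is a frequency: "Mean monthly HCRU (including frequency of hospitalizations, ER visits, OP visits". The other is binary: "Proportions of patients with Health care resource utilization (HCRU". Section 9.7.1 says the analysis will "compare the mean monthly (to account for variable follow-up time) per patient HCRU", both all-cause and asthma related. It names no model and no baseline covariate for that comparison.

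The baseline counterpart in Section 9.3.3, repeated in the Abstract, is "Baseline all-cause resource use (presence vs. absences of hospitalizations, or ER visits, or outpatient visits". Table 1 in Section 9.1 describes the same variable only as "All-cause hospitalizations, ER visits, outpatient visits" and gives no coding. Baseline covers at least six months of enrollment before index (Section 9.1, criterion 5).

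Other covariates bear on visit frequency indirectly. Section 9.3.3 has "Baseline overall medication history (polypharmacy defined as number of unique medications", Charlson comorbidities, a long list of single conditions, rescue medication use, ICS history and dose, and insurance type. Control status in Table 1 is binary and is triggered by an oral corticosteroid prescription, an asthma-related ER visit or an asthma-related hospitalization. It does not use outpatient visits.

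Balance is judged after 1:2 nearest-neighbor matching by p<0.05 and by SMD<0.1 (Section 9.1). If differences remain, Section 9.1 offers three routes: covariates in the Cox model, rematching on interaction terms, or stopping the study.

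**The concern.** Prior visit frequency is the direct baseline measure of mean monthly HCRU. Coding it yes/no discards the information that the endpoint uses: a patient with one outpatient visit in six months and a patient with twelve are treated as alike. The balance check looks only at variables in the plan, so it would report on the flag and not on the count.

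Matching is the only control of baseline confounding stated for this endpoint. The covariate remedy in Section 9.1 names only the Cox regression, which does not cover mean monthly counts. So if the two groups were already seen at different rates before index, the plan as written has no step that would show it and none aimed at correcting it. The result could be a difference in resource use credited to ICS+Tio or ICS/LABA that existed before either was started. Resource use is in the study title, so the comparison is likely to be read with some weight.

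**Working it through.** **Nothing to reproduce.** The documents give no visit rate, SD, effect size or target sample size for HCRU. The arithmetic below is an illustration, and every input is assumed.

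**Inputs (assumed).** Outpatient visits in six months are negative binomial (gamma-Poisson) with shape k = 2. The mean is 6 in ICS/LABA and 6 × 1.25 = 7.5 in ICS+Tio, so the pre-existing rate ratio is 1.25. There is no treatment effect, each patient's underlying rate carries into follow-up, and controls are matched exactly on any visit (yes/no) and on nothing else. The only input from the plan is the SMD<0.1 rule.

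**Step 1, flag before matching.** P(no visit) = (k/(k+mean))^k.
- ICS/LABA: (2/8)² = 0.0625, so 93.8% have a visit.
- ICS+Tio: (2/9.5)² = 0.0443, so 95.6% have a visit.
- SMD = (0.9557 − 0.9375)/√[(0.9557×0.0443 + 0.9375×0.0625)/2] = 0.0182/0.2247 = 0.08. This meets the rule.

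**Step 2, count before matching.** Variance = mean + mean²/k.
- ICS/LABA: 6 + 18 = 24. ICS+Tio: 7.5 + 28.125 = 35.625.
- SMD = 1.5/√[(24 + 35.625)/2] = 1.5/5.46 = 0.27. This fails the rule.

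**Step 3, after exact matching on the flag.** The flag's SMD is now 0.
- Expected six-month rate of an ICS/LABA patient with no baseline visit: k/(k/mean + 1) = 2/(2/6 + 1) = 1.5.
- With at least one visit: (6 − 0.0625×1.5)/0.9375 = 6.3.
- Matched ICS/LABA mean: 0.9557×6.3 + 0.0443×1.5 = 6.09.
- Residual ratio: 7.5/6.09 = 1.23. Excess: (7.5 − 6.09)/6 = 0.24 visits per month.
- Share of the log rate ratio left: ln(1.232)/ln(1.25) = 0.94.

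**Step 4, the count after that matching.** Matched ICS/LABA mean baseline count: 0.9557×6/0.9375 = 6.12. Variance: 0.9557×(24 + 36)/0.9375 − 6.12² = 23.8. SMD = (7.5 − 6.12)/√[(35.625 + 23.8)/2] = 0.25. The count would still fail a rule that the flag passes at 0.

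**Range of assumptions.** For means of 2 to 6 visits, shapes 1 to 2 and pre-existing ratios 1.1 to 1.5, matching on the flag alone leaves 78% to 94% of the log rate ratio. The residual ratio is 1.08 to 1.09 when the true ratio is 1.1, 1.19 to 1.23 when it is 1.25, and about 1.39 to 1.47 when it is 1.5. For a rare visit type (mean 0.1, about 9% with any visit), 90% to 95% is left. The loss therefore does not depend on almost everyone having a visit.

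**The case against.** **Other covariates do part of the work.** Polypharmacy is itself a count. Comorbidities, control status, rescue use, ICS history and dose, insurance type, and diagnoses such as sinusitis, acute bronchitis and dyspnea can all track visit frequency. This stands. The illustration ignores them, so its residual is an upper-end figure, and a residual near zero cannot be excluded.

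**The imbalance is hypothetical.** A reader might infer that pre-existing differences do pass into the HCRU result. The documents give no baseline visit rate for either arm and no reason to expect either to be seen more often, so only the conditional statement is supported.

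**The flag may not be near-constant.** A reader might infer that nearly every patient has a visit, so that the flag carries no information. No section gives that share. Criterion 1 ("Patients with least two asthma diagnosis (ICD 9 CM: 493.xx or ICD 10: J45-J45.999) will be included") is not tied to the six-month baseline or to a type of visit. The point does not need this claim, as the rare-visit case above shows.

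**The coding is not settled.** A reader might infer one composite flag. The wording in Section 9.3.3 also allows three separate flags, and Table 1 leaves the coding open. Either reading of Section 9.3.3 is presence/absence, so the gap in frequency remains.

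**Adjustment is not ruled out.** The Abstract refers to time-varying exposure covariates for all endpoints and to a regression, and Section 9.1 allows rematching on interaction terms. Neither brings in a baseline visit count. The accurate statement is that no baseline-adjusted HCRU model is specified.

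**Conclusion.** The point holds as a cheap improvement to one secondary endpoint. Mean monthly HCRU is a frequency, its baseline counterpart is matched as presence or absence, asthma-related outpatient use is in no covariate list, and the balance check would not reveal a difference in counts. If such a difference exists, the part not captured by the other covariates would appear as a treatment difference.

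Its actual size is unknown. The ratio of about 1.23 rests on a negative binomial model, a pre-existing ratio of 1.25, full carry-over of each patient's rate into follow-up, and the flag as the only matching variable.

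The scope is narrow. The proportion-with-HCRU endpoint is less affected, since a yes/no baseline is a closer counterpart to it. A reader might extend the point to time to first severe exacerbation. The argument here concerns visit frequency and gives no ground for doing so.

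**What to change.** In Section 9.3.3, Table 1 and the Abstract, replace the presence/absence variable with separate baseline counts: hospitalizations (0/1/2+), ER visits (0/1/2+) and outpatient visits (continuous or in quartiles). Add the baseline count of asthma-related outpatient visits. State the coding identically in all three places, and include these counts in the SMD<0.1 check.

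A six-month count measures the underlying visit rate with error, so matching on it removes more than the flag does but not everything. As an optional complement, Section 9.7.1 could name a count model for HCRU with the baseline count as covariate and follow-up time as offset.

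The counts come from the same claims that the flags need. The cost is a few more propensity-score terms and possibly slightly fewer matches. Section 9.5 gives 921,804 ICS/LABA against 17,882 tiotropium patients after the COPD exclusion, a ratio of 921,804/17,882 = 51.5 where 1:2 matching needs 2. That ratio comes before the remaining criteria and the concurrent-ICS restriction, so the ratio in the final matching pool is not known.

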Pneumonia	Identified using appropriate ICD codes. Coded as binary (yes/no) variables	PSM
Acute bronchitis	Identified using appropriate ICD codes. Coded as binary (yes/no) variables	PSM
Dyspnea	Identified using appropriate ICD codes. Coded as binary (yes/no) variables	PSM
Alcohol dependence	Identified using appropriate ICD codes. Coded as binary (yes/no) variables	PSM
Smoking dependence	Identified using appropriate ICD codes. Coded as binary (yes/no) variables	PSM

Using propensity score matching (PSM) technique, we will develop matched cohorts of patients between the ICS+Tio and ICS/LABA groups. We will conduct 1:2 matching using nearest neighbor matching approach. Upon completion of matching, we will assess whether the cohorts are balanced by examining the statistically significant differences at $p < 0.05$. We will also assess balance by calculating standardized mean differences (SMD). An SMD < 0.1 will be considered balanced. Follow-up time will be calculated between index date and 'Censor date' which will be defined as the date of either one of the following events: 1. Date of first exacerbation, 2. Date of medication switch, 3. Discontinuation of medication (defined as date of prescription claim plus days' supply, plus 50% additional days), 4. Enrollment end date, or 5. Last date available in the dataset/End of study period. In this "new user", study design, primary analysis will be an "as-treated" analysis. In order to attribute events and outcomes to patients during the time that they are exposed to treatment (based on days-supply of prescription claims + a buffer window) as well as account for differences in inter-group adherence levels, we will use a time-varying covariate approach to classify drug exposure time for each comparator drug during follow up. This approach has been chosen to minimize bias based on potentially large differences in medication adherence rates, by only attributing outcomes to the time in which patients have medication in their possession based on days' supply as described below. For each individual study drug, we will identify and define medication exposure and non-exposure windows during the follow-up time for each medication using the date of prescription filled plus the days' supply listed on the prescription claim plus 50% additional days (to account for residual doses in canister, poor real-world adherence and latency of drug effects). For example, exposure start and stop dates

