9.5 STUDY SIZE

There are 25,291 patients with a prescription claim for tiotropium (1.25mcg, October 2015-May 2020) identified for analysis and 1,125,657 patients with ICS/LABA prescription claims (July 2014-May 2020). After excluding patients with COPD there are 17,882 patients in the Tio group and 921,804 patients in the ICS/LABA group. Further inclusion-exclusion criteria as well as restricting the Tio group to those with concurrent ICS monotherapy, will be applied to arrive at the final sample.

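### Smoking is captured only by dependence codes in the 6-month baseline, which may leave residual confounding by smoking history that the balance checks cannot detect

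*Combined protocol and SAP*

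**What the plan says.** Section 9.3.3 lists the propensity score covariates. The only smoking item is "Smoking dependence during baseline identified using ICD 9 305.1 and ICD 10 F17.xx", and the abstract repeats it. Table 1 in section 9.1 carries the same item as "Smoking dependence", defined as "Identified using appropriate ICD codes. Coded as binary (yes/no) variables", so there are two levels and no category for past use.

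The baseline is 6 months. Section 9.1 refers to it in the exclusion "Patients with prior Tio or ICS/LABA use during the 6-month baseline period will be excluded" and sets the minimum pre-index enrolment to match: "Patients will be required to have enrollment for at least 6 months prior to ICS+Tio or ICS/LABA use". No longer look-back is stated for smoking.

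Balance after 1:2 nearest-neighbour matching is judged on the listed covariates, by tests at p < 0.05 and by SMD < 0.1. If differences remain, section 9.1 lets the study team adjust for them in the Cox model, build interaction terms to match on, or stop the study. The only sensitivity analysis stated varies the exposure window (0% and 100% additional days). Section 9.9 mentions patient misclassification and limited clinical history in general terms and does not name smoking.

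**The concern.** The covariate detects a dependence diagnosis recorded in a short window. A patient who stopped smoking years ago, or who smokes without a dependence diagnosis, falls in the same category as a never-smoker unless a qualifying code was billed in those 6 months. No other listed covariate identifies smoking: a cessation-drug claim would add to the count of unique medications but would not be recognised as such.

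Smoking history could plausibly influence both the choice of add-on drug and the risk of exacerbation. If so, matching on the coded variable balances the code and not the history. The plan's checks examine measured covariates only, so the decision to adjust, re-match or stop could not be triggered by such an imbalance. At stake is a modest bias in the primary hazard ratio. It matters most if the true ratio is close to 1, which is possible given that section 7 describes similar exacerbation responses in the randomised trials.

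**Working it through.** The plan gives no smoking prevalence and no assumed effect of smoking, so it has no figure of its own to reproduce. Two checks are possible.

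**1. Does the plan contain evidence of channelling?**

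Inputs from section 9.5:

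- Tiotropium before the COPD exclusion: "There are 25,291 patients with a prescription claim for tiotropium (1.25mcg, October 2015-May 2020) identified for analysis". Remaining afterwards: 17,882.
- Comparator before the COPD exclusion: "1,125,657 patients with ICS/LABA prescription claims (July 2014-May 2020". Remaining afterwards: 921,804.

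Shares removed:

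- Tiotropium: (25,291 − 17,882) / 25,291 = 7,409 / 25,291 = 29.3%.
- ICS/LABA: (1,125,657 − 921,804) / 1,125,657 = 203,853 / 1,125,657 = 18.1%.
- Ratio: 0.2930 / 0.1811 = 1.62.
- SMD = (p1 − p0) / √{[p1(1 − p1) + p0(1 − p0)] / 2} = 0.1119 / 0.4216 = 0.27.

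Coded COPD was therefore more frequent among tiotropium claimants before restriction. This is a statement about COPD, not about smoking, and about patients who are then removed.

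**2. How large could the bias be?**

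For an unmeasured binary confounder with prevalence p1 in ICS+Tio and p0 in ICS/LABA, and risk ratio RR for exacerbation, the hazard ratio is multiplied by approximately

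[1 + p1(RR − 1)] / [1 + p0(RR − 1)].

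Here p1 and p0 are the prevalences of uncoded smoking history in the matched cohorts. All values below are assumptions; none is in the documents. The ranges are p1 20-30%, p0 15-20%, RR 1.2-1.5.

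| p1 v p0 | RR | Calculation | Bias factor | SMD of the hidden variable |
|---|---|---|---|---|
| 20% v 20% | any | equal terms | 1.00 | 0 |
| 20% v 15% | 1.2 | 1.04 / 1.03 | 1.010 | 0.13 |
| 30% v 20% | 1.5 | 1.15 / 1.10 | 1.045 | 0.23 |
| 30% v 15% | 1.5 | 1.15 / 1.075 | 1.070 | 0.37 |

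The last SMD is 0.15 / √[(0.21 + 0.1275) / 2] = 0.15 / 0.411 = 0.37.

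Two points follow. The assumed ranges include the case of no bias. And a gap as small as 20% v 15% already exceeds the plan's own limit of 0.1 without being seen, because the variable is not measured.

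**The case against.** A reader might infer that smoking-related risk is channelled to tiotropium and stays unbalanced after matching. The documents do not support that. They report no smoking prevalence by group and no post-match balance. The 29.3% v 18.1% contrast comes from all claimants, before the restriction to concurrent ICS and the other criteria, and over different calendar windows (from October 2015 v from July 2014). The patients behind it are excluded, and taking more COPD patients out of the tiotropium group would be expected to narrow a smoking gap rather than preserve it.

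The plan also has real mitigation. The exclusion "Patients with least two diagnosis of COPD at any time during the study period will be excluded" reaches COPD first coded after the index date. Matching covers plausible correlates of smoking history: age, Charlson comorbidities, cardiovascular disease, cancer, pneumonia, acute bronchitis, dyspnea, alcohol dependence, control level and rescue use. What matters is the difference left after conditioning on these, which should be smaller than the raw difference if they carry information on smoking. The primary endpoint needs a primary diagnosis of asthma, so events coded to another respiratory disease do not count.

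Nor is it right that every former smoker is scored as a non-smoker. The text says dependence and takes the whole F17.xx family, so any sub-code for past dependence recorded in baseline would count as yes.

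All of this stands and limits the point. It does not close the gap. Patients with a single COPD code remain in the cohort, correlates are not a measurement of smoking, and past or non-dependent smokers without a qualifying code are still misclassified with nothing planned to show or bound the effect.

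**Conclusion.** The definition is narrow, and residual confounding by smoking history is possible and would be invisible to the planned balance checks. That it actually occurs is not shown.

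Under the assumed prevalences and risk ratios, the bias factor runs from 1.00 to about 1.07. A true hazard ratio of 0.90 would be estimated at between 0.90 and 0.90 × 1.07 = 0.96. The direction, probably against ICS+Tio, rests on uncoded smoking history being more common in that group and raising exacerbation risk. The documents support the first only indirectly and give no figure for the second. The point is a low-cost improvement in confounder control, not a defect that threatens the study. No sample-size or power figure is affected, since the plan states none.

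**What to change.** Change the smoking definition consistently in section 9.3.3, the abstract and Table 1:

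- Within the same fixed 6-month baseline, add history-of-tobacco and tobacco-use codes (V15.82, Z87.891, Z72.0) and smoking-cessation drug claims. These codes are not in the documents and should be checked against the coding manuals.
- Enter dependence or current use, and past use, as two separate yes/no variables in the propensity score. State in advance to which of the two a cessation-drug claim belongs.
- Report the SMD of each before and after matching.
- As a sensitivity analysis, use all available pre-index data for smoking and enter pre-index enrolment length as a covariate. The fixed window should remain primary, because with an open look-back the chance of finding a code depends on how long the patient was enrolled.
- Name residual smoking misclassification in section 9.9.

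The cost is a longer code list and one more matching variable, all from claims already being extracted. Past smoking will still be captured incompletely, so the change reduces the misclassification without removing it.

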Proprietary confidential information © 2021 Boehringer Ingelheim International GmbH or one or more of its affiliated companies for a patient with a prescription claim with 30 days supply on January 1st will be January 1st and February 15th respectively (30 days' supply +15 days). We will run sensitivity analyses on the exposure window using 0% and 100% additional days. These time varying exposure covariates will be included in the Cox PH regression.

If statistical differences are found after PSM, then the study team will make a determination to either include them as covariates in the regression analysis (Cox PH), or develop interaction terms to match on, or discontinue the study. In the event of study discontinuation, partial results (all analysis leading up to and including PSM) will be provided in a final report.

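### Both Cox models omit baseline risk factors by default, so as-treated censoring that depends on baseline risk differently by arm can bias the HR even after perfect matching

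*Combined protocol and SAP*

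**What the plan says.** Section 9.3.1 makes the matched cohort the main term: "After PSM, the cohort group will be the key predictor for the Cox PH regression to assess the primary outcome". Section 9.3.3 adds one more: "we will include time varying medication exposure as a covariate in the regression". The abstract applies the exposure term to the primary and all secondary endpoints, so the model for moderate-or-severe exacerbation has the same form. No baseline variable is named for either model. Table 1 gives matching as the adjustment method for every baseline variable, and the 33 items in 9.3.3 are introduced by "The covariates included in the PSM will be".

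The only route for a baseline variable into the Cox model is in 9.1: "If statistical differences are found after PSM, then the study team will make a determination to either include them as covariates". The alternatives are to match on interaction terms or to stop the study. Balance is judged in two ways: "we will assess whether the cohorts are balanced by examining the statistically significant differences at" p < 0.05, and "An SMD < 0.1 will be considered balanced". The plan does not say which governs when they disagree.

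Follow-up in 9.1 is as-treated. It ends at first exacerbation, switch, discontinuation (claim date plus days' supply plus 50%), end of enrollment or end of data. The only sensitivity analysis stated there changes the exposure window to 0% or 100% extra days. Section 9.9 does not list informative censoring as a limitation.

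**The concern.** Propensity matching makes the arms comparable on the measured factors at index. It does not keep them comparable among patients still on treatment. If well controlled patients leave one arm sooner than the other, the patients still at risk in that arm become a higher-risk group. A model with group alone reads this as a drug effect.

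The exposure term is unlikely to repair it. In the main analysis the exposure windows and the discontinuation date use the same days' supply plus 50% rule, so nearly all follow-up should count as exposed and the term carries little information.

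Section 7 summarizes the randomized trials as showing similar responses, so the expected HR is near 1. There, a distortion of several percent can change the reading of the primary result. The decision to adjust is also made after balance has been seen.

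**Working it through.** The plan states no target HR, event rate, stopping rate or matched sample size, so there is no figure of its own to reproduce.

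**1. Drop-out after index, with perfect balance at index**

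The inputs are assumptions, except the 1:2 ratio (9.1: "We will conduct 1:2 matching using nearest neighbor matching approach", taken as one ICS+Tio to two ICS/LABA):
- true HR 1; 40% not well controlled in both arms
- severe event rate 0.04 per person-year if well controlled, multiplied by 2 or 3 if not
- stopping rate 3 per person-year, multiplied in the ICS+Tio arm by the factors in the table
- follow-up long enough that nearly everyone has stopped.

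For arm a (weight w = 1/3 or 2/3) and risk level z, let n_az(t) = w_a · p_z · exp{−(h_z + c_az)t} and d_az(t) = h_z · n_az(t). Summing over z gives n_a and d_a. The large-sample group-only log HR, b, solves

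∫ [d_1 − (d_1 + d_0) · n_1·e^b / (n_1·e^b + n_0)] dt = 0.

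| Stopping factor in ICS+Tio, well / not well controlled | Group-only HR, risk-factor HR 2 | Group-only HR, risk-factor HR 3 |
|---|---|---|
| 1.5 / 0.82 (strong) | 1.11 | 1.17 |
| 1.25 / 0.90 | 1.06 | 1.09 |
| 1.2 / 1.0 | 1.03 | 1.05 |
| 1.10 / 0.95 | 1.03 | 1.04 |
| 1.5 / 1.5 (arm difference only) | 1.00 | 1.00 |
| 0.82 / 1.5 (reversed) | 0.91 | 0.86 |

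Stratifying on the risk factor returns 1.00 in every row. A simulation of 1.5 million patients per scenario under the strong pattern gave 1.097 and 1.171 unadjusted, and 0.993 and 1.004 adjusted.

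The mechanism shows in who remains. Under the strong pattern, ignoring events, the ICS+Tio shares at six months are 0.4·exp(−3·0.82·0.5) = 0.117 not well controlled and 0.6·exp(−3·1.5·0.5) = 0.063 well controlled. Those not well controlled are then 0.117/0.180 = 65% of the arm, against 40% in ICS/LABA.

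**2. Residual imbalance at index**

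Take 44.5% against 40.0% not well controlled.
- SMD = 0.045 / √[(0.445·0.555 + 0.40·0.60)/2] = 0.091, below 0.1.
- False HR ≈ [1 + (h−1)·0.445] / [1 + (h−1)·0.40] = 1.445/1.40 = 1.03 for h = 2, and 1.89/1.80 = 1.05 for h = 3.

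The p < 0.05 test (two-sided assumed) would flag this difference from n ICS+Tio patients upward. With pooled proportion (0.445 + 2·0.40)/3 = 0.415,

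n = (1.96/0.045)² · 0.415 · 0.585 · 1.5 ≈ 691.

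The largest difference from 40% that escapes the test is 2.6 points at 2,000 ICS+Tio patients (false HR 1.02 to 1.03) and 1.7 points at 5,000 (1.01 to 1.02). Section 9.5 starts from 17,882 in the Tio group before further exclusions; the final number is not given.

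**The case against.** Matching on 33 covariates, fitting a group-only model and adjusting for whatever imbalance remains is a recognised design. Which model is primary and which is supportive is partly a matter of choice. That stands, and it is why this is a recommended improvement rather than an error that invalidates the analysis.

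A reader might infer that the plan accepts 44.5% against 40.0% as balanced, and so accepts a 3 to 5% false effect. The documents do not support this in general. The trigger in 9.1 is a statistical difference, and that test would catch this example from about 691 ICS+Tio patients upward. The example survives only in a smaller matched cohort, or if the SMD rule overrides the test, which the plan does not say. Even so, a flagged difference does not guarantee adjustment, because adjustment is only one of three options.

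A reader might also infer that the primary HR will be off by 5 to 15%, because 9.1 anticipates large adherence differences. That does not follow. Section 9.1 speaks of adherence differing between groups, and a difference by arm alone gives no bias here. Bias needs stopping to depend on risk differently by arm, and the documents give no rates for that. The strong pattern also assumes the two risk groups move in opposite directions at once.

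Finally, adjustment might be taken to make censoring independent. It does so only if stopping depends on nothing prognostic beyond the adjusted baseline factors. Patients who switch or stop because their asthma worsened after index remain a source of bias.

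**Conclusion.** The point holds. By default both Cox models contain only group and time-varying exposure, and baseline predictors enter only at discretion after balance has been seen. With censoring at switch and discontinuation, matching at index does not protect the HR if stopping depends on baseline risk differently by arm.

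The textual finding is firm; the size and sign of any bias are not. The range of 1.03 to 1.17, or its reversal below 1, rests on assumed stopping patterns, prevalence, event rate and a risk-factor HR of 2 to 3. Residual imbalance is a lesser reason to adjust, unless the matched cohort is small, the SMD rule governs, or several covariates lean the same way.

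**What to change.** In 9.3.3 and 9.7.1, state that both Cox models (severe; moderate-or-severe) always adjust, whatever the balance result, for a short fixed list:
- control status, which under Table 1 already includes asthma ER visits and hospitalizations, so these need no separate term
- rescue medication use
- ICS history
- ICS dose level
- other asthma medication
- age, continuous or in a few broad bands rather than the 5-year increments of Table 1
- season.

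Report the group-only model alongside. Add to 9.9 that adjustment removes only the bias explained by measured baseline factors, and that censoring driven by worsening after index is not corrected; that would need a further method such as censoring weights.

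The cost is a sentence or two of text and a few model terms. All the variables are already built for the propensity score. The downside is that the list must stay short if severe events are few.
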